3.2.5 Pharmacodynamic assessments

Blood and stratum corneum samples will be collected according to schedule of assessments to investigate the effect of nemolizumab on selected biomarkers, including but not limited to thymus and activation-regulated chemokine (TARC), IgE, IL6, IL8, and IL18.

3.2.6 Quality of life assessments

3.2.6.1 Dermatology Life Quality Index (DLQI)

DLQI is a validated 10-item questionnaire, covering domains including symptoms/feelings, daily activities, leisure, work/school, personal relationships and treatment. Subject will rate each question ranging from 0 (not at all) to 3 (very much), and the total score ranges from 0 to 30, with a higher score indicating a poorer quality of life (QoL). Please note that “Not relevant” is scored as 0, and Question 7, “prevented work or studying” is scored as 3. DLQI will be administered only to the subset of subjects who fluently speak a language in which the questionnaire is presented.

DLQI will be assessed at baseline, weeks 2, 12, 24, or early termination visit when applicable.

The DLQI score will be categorized as follows:

- 0-1 = no effect at all on subject’s life
- 2-5 = small effect on subject’s life
- 6-10 = moderate effect on subject’s life
- 11-20 = very large effect on subject’s life
- 21-30 = extremely large effect on subject’s life

The DLQI can be analyzed under 6 sub-scales, namely, symptoms and feelings (question 1 and 2), daily activities (question 3 and 4), leisure (question 5 and 6), work and school (question 7), personal relationships (question 8 and 9), and treatment (question 10).

For general inflammatory skin conditions a change in DLQI score of at least 4 points is considered clinically important.

Refer to Appendix 3 for details on scoring, data handling rules, and analysis on DLQI.

3.2.6.2 Hospital Anxiety and Depression Scale (HADS)

HADS is a validated questionnaire containing 14 items, 7 each for anxiety and depression. Subject will rate each question ranging from 0 to 3, and the total score ranges from 0 to 21 for each sub-scale. HADS will be administered only to the subset of subjects who fluently speak a language in which the questionnaire is presented.

For each sub-scale, the score will be categorized as follows:

- 0-7 = Normal
- 8-10 = Borderline abnormal (borderline case)
- 11-21 = Abnormal (case):

HADS will be assessed at baseline, weeks 12, 24, or early termination visit when applicable.

At a given visit, there must be responses to at least 6 out of 7 questions within each sub-scale of anxiety and depression. If fewer than 6 responses, then the sub-scale will be set to missing.

3.2.6.3 Sick leave/missed school day

Subjects who are employed or enrolled in school/university at baseline will be asked to report the number of missed work/school days due to AD since the last visit (or since the last 4 weeks at week 4) not including missed work/school days due to participation in this clinical trial.

3.2.6.4 EuroQoL 5-Dimension (EQ5D)

EQ5D is a validated questionnaire for the assessment of the general health state. It contains 2 parts: a descriptive system and a VAS. The descriptive system is made up of 5 dimensions: mobility, self-care, usual activities, pain/discomfort and anxiety/depression. The VAS consists of a vertical line where the subject can assess his or her own health status. EQ5D will be administered according to the schedule of assessments only to the subset of subjects who fluently speak a language in which the questionnaire is presented.

Refer to Appendix 4 for details on calculation of EQ5D index score.

4 STATISTICAL METHODS

4.1 Data Quality Assurance

All tables, figures and data listings (TLFs) to be included in the report will be independently checked for consistency, integrity and in accordance with standard PAREXEL procedures.

4.2 General Presentation Considerations

Unless otherwise stated, descriptive summaries will be presented by treatment group. In all tables the treatment groups will be presented in the order of Placebo, Nemolizumab 10 mg, Nemolizumab 30 mg, and Nemolizumab 90 mg. Comparisons on the difference between each nemolizumab group and placebo will be presented.

Continuous data will be summarized in terms of the mean, standard deviation (SD), median, minimum, maximum, lower quartile (Q1), upper quartile (Q3), and number of observations, unless otherwise stated. Where data are collected over time, both the observed data and change from baseline will be summarized at each time point. The minimum and maximum will be reported to the same number of decimal places as the raw data recorded in the database. The mean, median, Q1, and Q3 will be reported to one more decimal place than the raw data recorded in the database. The SD will be reported to 2 more decimal places than the raw data recorded in the database. In general, the maximum number of decimal places reported shall be four for any summary statistic.

Categorical data will be summarized in terms of the number of subjects providing data at the relevant time point (n), frequency counts and percentages. Percentages will be presented to one decimal place. A percentage of 100% will be reported as 100%. Percentages will not be presented for zero counts. Percentages will be calculated using n as the denominator. If sample sizes are small, the data displays will show the percentages, but any textual report will describe

frequencies only. Changes from baseline in categorical data will be summarized using shift tables where appropriate.

P-values greater than or equal to 0.001, in general, will be presented to three decimal places. However, if a p-value is only presented to four decimal places (by SAS) it will not be rounded again, but will be presented to four decimal places. P-values less than 0.001 will be presented as “<0.001”, and p-values greater than 0.999 will be presented as “>0.999”.

Confidence intervals (CIs) will be presented to one more decimal place than the raw data.

All report outputs will be produced using SAS® version 9.3 or a later version in a secure and validated environment. The outputs will be provided as individual TLFs in RTF format and all TLFs in one PDF bundle.

All statistical tests will be two-sided and will be performed at the 5% level of significance, unless otherwise stated.

Baseline

‘Baseline’ is defined as the last available assessment prior to the first administration of study drug, if it exists; otherwise, ‘baseline’ is defined as the last available assessment prior to date of randomization.

For diary data (pruritus NRS, PCS, Sleep disturbance NRS), the baseline values will be derived from data collected during the 7 days prior to the first administration of study drug. Baseline score will be the weekly prorated average of non-missing subject diary scores reported during the 7 days. A minimum of 4 daily scores out of the 7 days is required to calculate the weekly prorated average score.

Analysis Visit

Study day is relative to date of randomization. Day -1 is the day before randomization, and day 1 is date of randomization.

Assessments at early termination and unscheduled visits will be slotted based on the following visit window.

Period	Analysis Visit	Target day (relative to randomization)	Day ranges
Run-in	Screen	<1	<1
Treatment	Baseline	1	≤1
	Week 1	8	2-11
	Week 2	15	12-22
	Week 4	29	23-43
	Week 8	57	44-71
	Week 12	85	72-99
	Week 16	113	100-127

	Week 20	141	128-155
	Week 24	169	156-183
Follow-up	Week 28	197	184-211
	Week 32	225	>211

The diary reported during study will be classified into analysis visits as follows (i.e., during the 7 days prior to the target day of analysis visit. In this case, the target day of analysis visit is relative to date of the first administration of study drug.):

- Day -7 to -1 = Baseline
- Day 1 to 7 = Week 1
- Day 8 to 14 = Week 2
- Day 22 to 28 = Week 4
- Day 50 to 56 = Week 8
- Day 78 to 84 = Week 12
- Day 106 to 112 = Week 16
- Day 134 to 140 = Week 20
- Day 162 to 168 = Week 24
- Day 190 to 196 = Week 28
- Day 218 to 224 = Week 32

These analysis visits will be used in the calculations for all week-based parameters collected on subject's diary (e.g., pruritus NRS, PCS, Sleep disturbance NRS). Other non-diary data, such as EASI, IGA, BSA, SCORAD, DPS, DLQI, HADS, EQ5D, 5-D itch, missed work/school day, vital signs, body weight, clinical laboratory assessments, respiratory assessment/PEF, will be analyzed according to actual scheduled visits.

For efficacy and safety data (except clinical laboratory assessments), where two or more assessments (include both scheduled and unscheduled assessments) are available for the same visit interval, the one closest to the target visit date will be used for the summary and analyses. For clinical laboratory assessments, if repeated measurements are taken for either time point (scheduled visit), then the last measurement will be used for the value for that time point. Unscheduled labs will be included in listings, but not summaries of the data. All post baseline assessments, including repeated or unscheduled visits, will be used for potentially clinically significant (PCS) value determinations.

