Visit (V)	Screening/ D -28 to -15		Baseline/ D 1	W1	W2	W4	W8	W12	W16	W20	W24	W28	W32				
Week (W)			D8	D15	D29	D57	D85	D113	D141	D169	D197	D225					
Day (D)			± 1d	± 1d	± 1d	± 3d	± 5d	± 5d	± 5d	± 5d	± 5d	± 7d	± 7d				
Visit window (±d)																	
PK AND ADA ASSESSMENTS																	
PK samples		X	X	X	X	X	X	X	X	X	X	X	X	X	X	(X)	X
ADA samples		X	X	X	X	X	X	X	X	X	X	X	X	X	X	(X)	X
STUDY DRUG AND BACKGROUND THERAPIES																	
Randomization		X															
Subcutaneous study drug injection		X			X	X	X	X	X	X	X	X	X	X	X		
TCS dispensing (D) / Return (R) and moisturizer dispensing if necessary	D	D/R	D/R	D/R	D/R	D/R	D/R	D/R	D/R	D/R	D/R	D/R	D/R	D/R	D/R	D/R	D/R

^a Screening visit must be performed at least 14 days prior to the day 1 visit to ensure that each subject undertakes at least 14 days of TCS treatment prior to randomization.

^b Subjects are required to fast for at least 8 hours before the visit.

^c Assessments to be conducted at the unscheduled visit depend on the reason for the visit. PK and ADA analyses are obligatory at unscheduled visits for safety reasons.

^d Subjects discontinued before the week 24 visit should attend an early termination visit and a final visit 12 weeks after the last study drug injection.

^e Pruritus NRS and PCS to be recorded by subjects once daily in the evening. Sleep disturbance NRS to be recorded by subjects once daily in the morning.

^f DPS to be recorded by subjects at 2, 4, 8, 24, 48, and 72 hours after the study drug administration on day 1.

^g PEF will be measured for subjects with a medical history of asthma only.

^h Only for females of childbearing potential. Serum pregnancy test to be performed at screening visit, and urine pregnancy test for all other visits.

ⁱ Stratum corneum sample from lesional and non-lesional skin on day 1 and from lesional skin only at week 16.

LIST OF ABBREVIATIONS AND DEFINITIONS OF TERMS

Abbreviation	Term
°C	Degrees Celsius
°F	Degrees Fahrenheit
AD	Atopic Dermatitis
ADA	Anti-Drug Antibody
AE	Adverse Event
AESI	Adverse Event of Special Interest
ALT	Alanine Aminotransferase
AST	Aspartate Aminotransferase
AUC	Area under the Curve
BLQ	Below the Limit of Quantification
BSA	Body Surface Area
C _{max}	Maximum Concentration
CPK	Creatinine Phosphokinase
eCRF	electronic Case Report Forms
CRA	Clinical Research Associate
CRO	Contract Research Organization
CSO	Clinical Safety Officer
CYP450	Cytochrome P450
DLQI	Dermatology Life Quality Index
DMP	Data Management Plan

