7.1.1.5 Pruritus Numeric Rating Scale (NRS)

Pruritus NRS is a scale to be used by the subjects to report the intensity of their pruritus (itch) during the last 24 hours (see APPENDIX 5). Subjects will receive instructions on how to record their pruritus NRS scores on an electronic device, and will complete the assessment once daily in the evening throughout the clinical trial (including the run-in and the follow-up period).

Subjects will be asked the following questions in their local language:

- For average itch intensity: “On a scale of 0 to 10, with 0 being ‘no itch’ and 10 being ‘worst itch imaginable’, how would you rate your itch overall during the previous 24 hours?”
- For maximum itch intensity: “On a scale of 0 to 10, with 0 being ‘no itch’ and 10 being ‘worst itch imaginable’, how would you rate your itch at the worst moment during the previous 24 hours?”

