7.1.1.7 Dynamic Pruritus Score (DPS)

The 9-point DPS is a dynamic scale to be used by subjects to evaluate the change of their pruritus compared with an earlier time point (i.e. before injection on Day 1). The scale ranges from 0 (strongly worsened pruritus) to 8 ([almost] no pruritus anymore), including intermediate marks for slightly improved/worsened, moderately improved/worsened, and rather improved/worsened (Ständer 2016; see APPENDIX 7). Subjects will receive instructions on how to record their DPS score on an electronic device displaying the electronic version of the scale in their local language, and will complete the assessment 2, 4, 8, 24, 48 and 72 hours after study drug injection on day 1.

7.1.1.8 *5-D itch scale*

The 5-D itch scale is a multidimensional measure of itching that has been validated in patients with chronic pruritus (Elman 2010, see APPENDIX 8). The five dimensions included in the scale are degree, duration, direction, disability and distribution. The score for each of the five domains separately will then be summed up to obtain a total 5-D score, which ranges between 5 (no pruritus) to 25 (most severe pruritus). The 5-D itch scale will be administered at baseline and week 2.

7.1.1.9 *Sleep disturbance Numeric Rating Scale (NRS)*

The sleep disturbance NRS is a scale to be used by the subjects to report the degree of their sleep loss related to AD (see APPENDIX 9). Subjects will receive instructions on how to record their sleep disturbance NRS scores on an electronic device, and will complete the assessment once daily in the morning throughout the clinical trial (including the run-in and the follow-up period).

Subjects will be asked the following questions in their local language:

- On a scale of 0 to 10, with 0 being ‘no sleep loss related to signs/symptoms of AD’ and 10 being ‘I cannot sleep at all due to the signs/symptoms of AD’, how would you rate your sleep last night?”

7.1.2 **Efficacy endpoints**

7.1.2.1 *Primary endpoint*

Percent change from baseline in EASI to week 24

7.1.2.2 *Secondary efficacy endpoints*

- Proportion of subjects achieving IGA success (defined as IGA 0 [clear] or 1 [almost clear]) at each visit up to week 24
- Percent change from baseline in EASI at each visit up to week 24
- Absolute and percent change from baseline in weekly average of the peak and average pruritus NRS at each visit up to week 24

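### The Week 1 diary average includes the injection day, whose sleep score is wholly and itch scores partly pre-dose, so the Week 1 effect is diluted

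*SAP*

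**What the plan says.** SAP 4.2 (Analysis Visit) assigns diary entries to visits by a fixed rule: entries made "during the 7 days prior to the target day of analysis visit", where "the target day of analysis visit is relative to date of the first administration of study drug". Day 1 is therefore the day of the first injection. The resulting list includes "Day -7 to -1 = Baseline" and "Day 1 to 7 = Week 1". The list covers pruritus NRS, PCS and sleep disturbance NRS, and a weekly average needs at least four entries.

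The protocol fixes when each diary is completed and what it recalls:

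- Schedule of assessments (Table 2, footnote e): "Sleep disturbance NRS to be recorded by subjects once daily in the morning".
- Protocol 7.1.1.9, the sleep item: "how would you rate your sleep last night".
- Table 2, footnote e: "Pruritus NRS and PCS to be recorded by subjects once daily in the evening".
- Protocol 7.1.1.5, the peak itch item: "how would you rate your itch at the worst moment during the previous 24 hours". The average-itch item and the PCS (Appendix 6) also recall 24 hours.
- Protocol 8.1: study drug is given last, after patient-reported outcomes, investigator assessments and blood sampling.

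Neither document excludes the Day 1 diary entry or moves it to another window.

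**The concern.** The Day 1 morning sleep score is about the night before the injection, so it holds no treatment effect, yet it is averaged into Week 1 as on-treatment data. The Day 1 evening itch scores mix hours before and after the injection. In every arm the Week 1 average thus contains some baseline, which pulls the differences from placebo toward zero.

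SAP 4.2 also sits awkwardly with itself. Its text derives diary baseline from data collected in the 7 days before first administration. The Day 1 sleep entry precedes that administration but is listed under Week 1. The separate window table for early-termination and unscheduled assessments puts Day 1 in baseline and starts Week 1 at Day 2.

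Week 1 has some weight in this trial. SAP 4.7 lists percent change in weekly peak NRS and the 4-point peak NRS response for analysis at each visit up to Week 24. SAP 4.7.3.4 applies the MMRM to peak and average NRS at each visit. Protocol 3.4 treats rapid itch relief as a goal in its own right and uses it to justify the loading doses.

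**Working it through.** **1. Reproduce the SAP's windows.** The rule gives first day = target day − 7 and last day = target day − 1, with target days from the visit table in SAP 4.2. Week 1 (target 8) gives Days 1 to 7, Week 2 (15) gives 8 to 14, Week 4 (29) gives 22 to 28, and Week 24 (169) gives 162 to 168. All ten post-baseline windows reproduce. Day 1 is in Week 1 because the rule puts it there, not through a slip in the list.

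**2. Pre-dose share of the Day 1 entry, s.** For sleep, s = 1. For itch, let h be the hours from injection to evening entry; then s = (24 − h)/24. The share is above one half only when h is under 12. The documents give no clock time for either event. I assume injection from 08:00 to 16:00 and entry from 18:00 to 23:00.

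**3. Dilution.** For a constant daily effect and n diary entries in the week, dilution = s/n.

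| Case | h | s | n = 7 | n = 4, one being Day 1 |
|---|---|---|---|---|
| Itch: injection 08:00, entry 23:00 | 15 | 9/24 = 37.5% | 5.4% | 9.4% |
| Itch: 09:00, 22:00 | 13 | 11/24 = 45.8% | 6.5% | 11.5% |
| Itch: 11:00, 20:00 | 9 | 15/24 = 62.5% | 8.9% | 15.6% |
| Itch: 16:00, 18:00 | 2 | 22/24 = 91.7% | 13.1% | 22.9% |
| Sleep; ceiling for itch | – | 100% | 14.3% | 25.0% |

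When s = 1, the full-diary Week 1 effect is 6/7 of the Day 2 to 7 mean effect, whatever the time course. As an illustration, a true Week 1 difference of 20 percentage points would appear as 20 × (1 − 0.054) = 18.9 to 20 × (1 − 0.131) = 17.4 for itch. At the ceiling it would appear as 20 × 6/7 = 17.1.

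Proportionality to hours is only a proxy for the peak item. A worst-moment score cannot fall below the pre-dose worst moment within its recall period, so the loss can exceed the hour share, up to the ceiling.

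**4. The 4-point response.** If the Day 1 score equals baseline and the diary is full, a subject's weekly improvement is 6/7 of the mean improvement over Days 2 to 7. Reaching 4 then needs 4 × 7/6 = 4.67 over those days. A subject who improves by 4.0 to 4.66 counts as a non-responder. This is the worst case.

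**5. Power, as an upper limit on the loss.** The documents give no SD for NRS. Take a comparison with 80% power at 50 per arm and two-sided 5%; its expected z is 1.96 + 0.84 = 2.80.

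- With the SD held fixed, 1/7 dilution gives 2.80 × 6/7 = 2.40, and power Φ(2.40 − 1.96) = 67%.
- A dilution of 5.4% gives 2.80 × 0.946 = 2.65, and power Φ(2.65 − 1.96), about 76%.
- If Day 1 merely repeated baseline, each full-diary change score would be multiplied by 6/7 and its SD with it. The test would not move.

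The bias in the estimate is therefore firmer than any loss of power.

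**The case against.** The strongest reply is that the rule is uniform, pre-specified and the same in all arms, and that it errs only toward no difference, so it cannot manufacture an early-onset claim. That is correct and keeps the point minor.

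Second, the part that is certain is not tested. Sleep is analysed at Week 24 and only described at other visits (SAP 4.7). Week 1 sleep does enter the sleep MMRM as a visit, but that model fits a separate treatment effect at each visit. PCS success is likewise tested only at Week 24 (SAP 4.7.3.7) and summarised elsewhere (SAP 4.7.4.5). This stands.

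Third, a reader might infer that most of the Day 1 itch recall is pre-dose. The documents do not establish it. The fasting requirement at baseline suggests a morning visit. An injection at 09:00 to 11:00 with an entry at 20:00 to 22:00 gives a share of 46 to 63%, which is about half.

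Fourth, onset has its own measure. The DPS is recorded 2 to 72 hours after the Day 1 injection, against itch before that injection (Protocol 7.1.1.7). It is descriptive, but this window does not affect it.

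None of this explains why a score known to be pre-dose should count as on-treatment.

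**Conclusion.** The point holds as a small, avoidable dilution at one secondary time point. For sleep it is exact: 1/7 (14%) with a full diary. For itch it is about 5 to 13%, given the assumed clock times and proportionality to recall hours, with a ceiling of 14%. The 25% figure applies only to a subject with exactly four entries, one of them Day 1.

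It touches the tested Week 1 pruritus NRS contrasts and 4-point response, and the descriptive Week 1 sleep and PCS summaries. Two stronger readings are not supported. One is that itch loses a full 14% or more as a matter of course. That needs a Day 1 entry with no treatment effect at all, which the text guarantees only for sleep. The other is that the main efficacy conclusions are at risk. The primary endpoint is EASI at Week 24, no window from Week 2 onward contains Day 1, and all Week 24 endpoints are unaffected.

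**What to change.** In SAP 4.2, define Week 1 as Day 2 to Day 7 for pruritus NRS, PCS and sleep NRS, and keep the minimum of four entries. With a constant effect this restores the Week 1 sleep contrast from 6/7 to the whole effect, and the itch contrast from about 87 to 95% to the whole.

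Leave every later window as it is. Moving them all by one day (Week 4 to Days 23 to 29, for example) would bring in evening entries made after the next injection.

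For the Day 1 morning sleep score, choose one of two rules:

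- leave it out of both baseline and Week 1; or
- define the sleep baseline as Day -6 to Day 1 (morning entry), which is seven days.

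Adding Day 1 while keeping Day -7 would make eight days and conflict with the SAP's own seven-day baseline. The second option also gives sleep a different baseline window from NRS and PCS, which the SAP would need to state.

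The cost is one line of the window list, plus a line for sleep, and one fewer diary day. Slightly more Week 1 averages will be missing, because four entries must come from six days rather than seven. Under SAP 4.7.1.3 a missing value counts as non-response, so the affected subjects would become Week 1 non-responders. Reporting the number of missing Week 1 averages by arm would make this visible.

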4.3 Study Subjects

4.3.1 Disposition of Subjects

A clear accounting of the disposition of all subjects who enter the study will be provided, from screening to study completion.

The following subject disposition summaries will be produced:

- The number of subjects screened (Analysis population: All Subjects)
- Subjects Randomized by clinical site and overall (Analysis population: Screened Subjects)
- Screen failures (Analysis population: Screened Subjects)

The following summary will be produced for ITT population.

- The number of subjects randomized
- The number and percentage of subjects treated (with at least one dose of study drug)
- The number and percentage of subjects randomized but not treated (not taken any dose of study drug)
- The number and percentage of subjects who temporarily discontinued the study treatment and reasons for discontinuation
- The number and percentage of subjects who permanently discontinued the study treatment and reason of discontinuation
- The number of subjects completing study treatment (defined as completing week 24 visit)
- The number of subjects completing the study
- The number of subjects who discontinued from the study and reason of discontinuation
- A Kaplan-Meier plot of the time to permanent study treatment discontinuation will be provided. Subjects who did not discontinue from the study drug will be censored at their last dose of study drug (Analysis population: ITT).
- A Kaplan-Meier plot of the time to study discontinuation will be provided. Subjects who did not discontinue from the study will be censored at the date of study completion or the last visit date on the study (Analysis population: ITT).
- Time (days) to permanent discontinuation of study drug by reasons for discontinuation will be displayed graphically in subjects having permanently discontinued study drug.
- Time (days) to study discontinuation by reasons for discontinuation from study will be displayed graphically in subjects having discontinued study.

By-subject listings of eligibility details, randomization details, visit dates and withdrawal/study completion details (including reason for discontinuation and duration of treatment prior to discontinuation) will be provided.

